9.0 Risks and Benefits

9.1 Describe and assess any potential or known risks and discomforts, including possible loss of confidentiality, and assess their likelihood and seriousness. Also describe precautions to decrease the likelihood of harm and procedures to deal with harms if they occur. NOTE: Risks or harms can be physical, financial, social, or legal. They may involve breaches of

confidentiality and privacy. Do not include the risks of usual care unless usual care is part of the research interventions being performed.

Physical

A low carbohydrate diet may cause side effects, particularly during the first several weeks. These include:

1. Constipation: this is a common side effect, which will be managed by instructing individuals to increase their consumption of water and low-carbohydrate, fiber-rich foods such as leafy greens.
2. Headaches: this is a likely side effect, which will be managed by instructing individuals to increase their water and salt consumption.

There is also a small risk patients may experience harm or injury if they increase their physical activity as a result of taking part in this program.

Psychological - (For Example: Loss of privacy and confidentiality may cause psychological issues.)

There is a potential risk of loss of data confidentiality, which could have psychological risks. We will mitigate this risk by using a secure, HIPAA compliant, crosswalk file linking participant IDs and direct identifiers.

Participants may be concerned about their risk for developing type 2 diabetes. We will ease their anxiety by emphasizing that type 2 diabetes is a preventable condition and that this intervention is one way to help them to reduce their risk.

Social and economic - (For Example: Loss of confidentiality may cause social or economic duress though the unlikely risk is low.)

There is a potential risk of loss of data confidentiality, which could have social or economic consequences, although this risk is low.

9.2 Describe any risk of discovering abnormal findings and how you will inform the subject and/or the subject's primary care provider.

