Methods: We will recruit up to 30 patients with body mass index ≥ 25 kg/m² and prediabetes (defined as hemoglobin A1c [A1c] 5.7-6.4%) from the Ann Arbor VA primary care clinic. Participants will be identified by chart review and invited to participate by postal letter. Individuals that do not opt-out of study contact will be screened for eligibility by telephone call. Interested and eligible participants will be invited to attend an in-person information session. During this session, they will receive information about the dietary intervention; written informed consent will be obtained at this time. Study participants will attend a total of 24 group-based classes over the course of 1-year (not including initial information session). Body weight will be measured at each session. At baseline, 6-months, and 12-months, we will measure waist circumference, A1c, lipid levels, and self-reported outcomes including quality of life, mood, hunger, cravings, physical symptoms, and medication use/changes. Primary outcomes will be feasibility (e.g., enrollment, retention) and acceptability (e.g., session attendance, qualitative feedback). Secondary outcomes will change in weight, achievement of $\geq 5\%$ body weight loss, change in A1c, and change in lipid levels. During semi-structured interviews conducted at 6-months and 12-months, we will explore participants' experiences with the program, barriers to and facilitators of adherence to a low-carbohydrate diet, and perspectives on ways to improve the intervention.

Impact/Implications: Through this study, we will demonstrate the feasibility and acceptability of a LC-DPP among Veterans with prediabetes. These data will inform a large-scale comparative effectiveness trial of LC-DPP versus VA-MOVE.

List of Abbreviations

LC-DPP – low-carb Diabetes Prevention Program

A1c – hemoglobin A1c

Contents

Protocol Title:5

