5.0 Study Procedures

5.1 Study Design

We will conduct a single-arm mixed methods pilot study to test the preliminary efficacy on weight loss of a LC-DPP among Veterans with prediabetes (as defined by the American Diabetes Association [ADA] ²⁴). We hypothesize that at least 50% of LC-DPP participants will achieve at least 5% weight loss at 12 months and that the average weight loss in the LC-DPP will be greater than the average weight loss among historical controls in VA MOVE!.¹¹

Our team previously adapted the Centers for Disease Control and Prevention's (CDC's) National Diabetes Prevention Program (NDPP) curriculum—a lifestyle change program similar to MOVE!—to teach participants to follow a low-carbohydrate rather than a low-fat diet. We pilot tested our low-carbohydrate Diabetes Prevention Program (LC-DPP) among adults with prediabetes at a single, academic medicine primary care clinic.

The LC-DPP curriculum was adapted from the CDC National Diabetes Prevention Program materials and consists of 16 weekly one-hour group sessions over first 6 months (i.e. core phase) and 8 one-hour group sessions once or twice a month over the next 6 months (i.e. maintenance phase). Importantly, our adapted curriculum will adhere to the CDC's Diabetes Prevention Recognition Program (DPRP) guidelines, which aim to maintain the integrity of the DPP in heterogeneous settings. The DPRP formally recognizes sites that achieve specific targets (e.g. session attendance, weight loss) through use of a CDC-approved curriculum. Therefore, our curriculum, if effective, may be eligible for CDC-approval, which would facilitate future dissemination of this intervention.

We will use a mixed-methods sequential explanatory design, which is to say that quantitative data and qualitative data will be collected in two consecutive phases within the study ²⁵. Specifically, in the first phase, we will collect and analyze the quantitative data (e.g. surveys, weight, A1c, lipids). In the second phase, we will collect and analyze qualitative data (e.g. semi-structured interviews). The rationale for this approach is that the quantitative data will provide a general overview of the intervention's efficacy and limitations, and the qualitative data will help to explain these findings by exploring participants' experiences and perspectives in more depth.

Intervention

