 - The researchers will minimize this risk by compensating participants for the time required to complete the surveys at 6 and 12 months and to complete blood draws at 0, 6, and 12 months.
- Blood draws:
 - Adverse effects of blood draw may include lightheadedness, dizziness, bruise or infection at blood draw site.
 - If participants experience any adverse effects, we will ensure that participants receive appropriate medical care

- Questionnaires:
 - Some of the questions may make participants feel uncomfortably or upset. All participants are free to decline to answer any questions they do not wish to answer and to discontinue participation at any time.
- Diet:
 - Participants may experience some side effects when first reducing the amount of carbohydrates in the diet. This may include constipation, headache, bad breath, and muscle cramps. These symptoms usually go away after the first couple weeks on the diet. Participants can speak with study staff and study physicians ([name]). We have also shared information with participants' primary care providers regarding the benefits and potential side effects of low-carbohydrate diets.
- Increase in physical activity:
 - Participants may experience harm or injury from exercise if they increase their physical activity as a result of participation. As there is no requirement for patients to engage in physical activity as part of this study and no physical activity will be encouraged other than that ordinarily encountered in daily life, we do not consider the risk to be above minimal. Participants will be encouraged to contact the study team and/or their PCP in the event of any adverse events.

As with any research study, there may be additional risks that are unknown or unexpected. We do not know if participants will get any benefits from taking part in this research study. However, possible benefits may include weight loss, decreased risk of diabetes, reduction in hemoglobin A1c. Participation in this study may also help the study team to design and test new ways to help more people prevent type 2 diabetes.

Participants will receive results of a hemoglobin A1c and cholesterol tests at 6 and 12 months.

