5.5 Study Evaluations

Quantitative Data source

a) Weight

Participants will be encouraged to self-monitor weight using a home scale although this

data will not be collected by the study team. In accordance with standard DPP operating procedure, participants will be weighed in a private room prior to each session and their weight will be recorded by a member of the study team.

b) Physical activity

In accordance with standard DPP operating procedure, participants will be encouraged to self-monitor physical activity minutes and to report this information to the lifestyle coach at the start of each session.

c) Laboratory metrics

We will evaluate change in A1c and lipids over the study period. Baseline laboratory studies will be obtained once individuals have consented to participate in this study. Repeat A1c and lipid levels will be drawn at 6 and 12 months.

d) Session attendance

Participants will be encouraged to attend all sessions and attendance will be recorded by the lifestyle coach.

e) Survey Data

At baseline, 6 months, and 12 months, study participants will be invited to complete a written survey. Paper copies will be given to individuals at session 15/16. Because we aim to obtain complete follow-up data, we will make efforts to collect survey responses from participants that are not present for session 15/16. We will send surveys to non-attendeess via postal mail. All individuals will be asked to return their survey to the study team via pre-paid envelope or in-person delivery. The survey will assess domains related to the following: global health and well-being; sleep; food cravings; stress eating; hunger; energy; mood; physical symptoms, neuropathic symptoms (e.g., tingling, burning in feet); side effects; and cost of food. At baseline, we will ask participants to provide sociodemographic characteristics. At 6 months and 12 months, participants will be asked to provide feedback about the study and will receive compensation for each survey.

Qualitative Data Sources

Participants will be encouraged to maintain a log of food intake and physical activity. Each week, the lifestyle coach will review the logs and provide individual feedback. We will retain copies of participants' logs from their first 2 weeks in the study and their last 2 weeks in the study. In this way, we can qualitatively assess changes in dietary habits and physical activity.

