Below is a list of reasons that people sometimes give for eating tasty foods and drinks such as:

- Sweets like chocolate, doughnuts, cookies, cake, candy, ice cream, other desserts.
- Salty snacks like chips, pretzels, and crackers.
- Fast foods like hamburgers, cheeseburgers, pizza, fried chicken and French fries.
- Sugary drinks like soda, sweet tea, milkshakes, and smoothies.

To forget y	Q3	1 =	Coping	Burgess,
Because it	Q4	Almost	score:	E. E.,
To cheer u	Q5	never/Ne	Average	Turan, B.,
To forget a	Q6	ver	of four	Lokken, K.
		2 = Some	responses	L., Morse,
		of the	.	A.. &

Energy Levels between Meals

In the past week, two hours after you ate BREAKFAST, how do you feel?

Alert	Q1	Answer	NA	NA
Energetic	Q2	choices 1		
Tired	Q3	through		
Brain fog o	Q4	7, with		
Food cravii	Q5	anchors		
Hunger	Q6	on 1, 7:		
Moodiness	Q7	1- Not at		
		all		
		7		

In the past week, two hours after you ate LUNCH, how do you feel?

Alert	Q8	Answer	NA	NA
Energetic	Q9	choices 1		
Tired	Q10	through		
Brain fod o	Q11	7, with		
Food cravii	Q12	anchors		
Hunger	Q13	on 1, 7:		
Moodiness	Q14	1- Not at		
		all		

Physical Symptoms

How often have you experienced the following over the past week?

Acne	Q1		NA	NA
Bad breath	Q2			
Bloating or	Q3			

Cold hands Q4
Constipation Q5
Diarrhea Q6
Dizziness Q7
Dry mouth Q8
Constant tiredness Q9
Food intolerance Q10

Headaches Q11

Heart palpitations or a racing heart Q12

Heartburn Q13

Joint or muscle pain Q14

Muscle cramps Q15

Nausea Q16

Trouble concentrating Q17

Weakness Q18

Hair loss Q19

Sexual problems Q20

Numbness (loss of sensation) in the feet, legs, or hands Q21

Tingling or prickling sensation in the feet, legs, or hands Q22

Not at all
1 day a week
2-3 days a week
4-5 days a week
6-7 days a week

Burning or shooting pain in the feet, legs, or hands

Q23

Blurred or deteriorating vision

Q24

Please describe any other psychological or physical symptoms that you experienced during the past month.

Q25

Participants may enter free text of whatever they choose.

Health
Global Health PROMIS Questionnaire:

Please respond to each item by marking one box per row

In	Q1	5-	Re-code:	PROMIS
In	Q2	Excellent	Q7 (pain	Health
general,		4- Very	on	Organizati
would		good	average):	on and
you say		3- Good	0 = 5	PROMIS
your		2- Fair	1,2,3 = 4	Cooperati
quality of		1- Poor	4,5,6 = 3	ve Group,
life is:			7,8,9 = 2	2008-
In	Q3		10 = 1	2012.
general,				https://w
how			Global	ww.iconq
would			Physical	uerms.org
you rate			Health	/sites/all/

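### The defined lipid outcome does not name LDL, a stated risk of the diet, and the past-week symptom checklist does not cover the early weeks in which side effects are expected

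*SAP*

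**What the plan says.** The Protocol file holds an IRB application and a protocol narrative, both with numbered sections; I name which is meant.

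**Lipids.**
- The narrative Abstract lists among the secondary outcomes "change in A1c, and change in lipid levels".
- Narrative 5.5, Laboratory metrics: "We will evaluate change in A1c and lipids over the study period".
- Narrative 5.5, Secondary Measures, gives the only operational definition: change in triglycerides and in the total-to-HDL cholesterol ratio, from baseline to 6 and 12 months.
- Narrative 3.0, Aim 2, lists triglycerides, cholesterol and HDL in an open-ended list.
- Narrative 6.0 says that LDL can rise on this diet, that lipids are monitored at 0, 6 and 12 months, and that medication or diet may be changed after results are known.
- The SAP analysis text names no lipid. It promises mean change and SD for every continuous outcome.

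**Symptoms.**
- IRB application 9.1: "A low carbohydrate diet may cause side effects, particularly during the first several weeks".
- Narrative 5.1, Risks and Benefits, Diet: "These symptoms usually go away after the first couple weeks on the diet".
- The SAP Physical Symptoms checklist asks "How often have you experienced the following over the past week". Its last item, free text on any other symptoms, reaches back one month.
- Narrative 5.5, Survey Data, sets surveys at baseline, 6 months and 12 months, and adds: "Paper copies will be given to individuals at session 15/16".
- The core phase is "16 weekly one-hour group sessions over first 6 months" (narrative 5.1).
- The early records kept are food and activity "logs from their first 2 weeks in the study and their last 2 weeks in the study" (narrative 5.5), not symptom records.

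**The concern.** The plan names two things that might go wrong on this diet: a rise in LDL, and side effects in the opening weeks. For the first, the defined outcome consists of quantities that can improve while LDL gets worse. For the second, the one structured instrument that can be read in the SAP asks about weeks well after the expected period. The checklist content fits: it includes constipation, headaches, bad breath, muscle cramps, diarrhea and weakness, all of which the protocol names. The difficulty is when it is given.

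At stake is what the pilot can report. The Abstract says the data will inform a large comparative trial. It does not list what that trial needs; that LDL change and early tolerability would help in planning it is my judgement. Both also bear on acceptability, since participants in the prior pilot wanted more education to ease concerns about dietary fat and cholesterol (narrative 5.2).

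**Working it through.** The plan gives no figure of its own to reproduce here.

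**1. Can the ratio and triglycerides stand in for LDL?** Assumption: LDL = TC - HDL - TG/5 (TC total cholesterol, TG triglycerides, mg/dL). The documents do not say how LDL is obtained. With R = TC/HDL this becomes LDL = HDL × (R - 1) - TG/5. R and TG therefore leave LDL undetermined until HDL is known. At R = 4.30, each 1 mg/dL of HDL moves LDL by 3.3. The values below are hypothetical.

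| | TC | HDL | TG | R | LDL | LDL change |
|---|---|---|---|---|---|---|
| Baseline | 200 | 45 | 150 | 4.44 | 200 - 45 - 30 = 125 | |
| Follow-up A | 193.5 | 45 | 110 | 4.30 | 193.5 - 45 - 22 = 126.5 | +1.5 |
| Follow-up B | 215 | 50 | 110 | 4.30 | 215 - 50 - 22 = 143 | +18 |

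A and B give identical results on the defined outcome.

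**2. Does Aim 2 recover the loss?** The formula is linear, so mean LDL change = mean TC change - mean HDL change - (mean TG change)/5, if all three come from the same participants and Aim 2's cholesterol means total cholesterol.
- A: -6.5 - 0 + 8 = +1.5.
- B: 15 - 5 + 8 = +18.

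The mean is recovered. The SD is not. Writing Δ for change, Var(ΔLDL) = Var(ΔTC) + Var(ΔHDL) + Var(ΔTG)/25 - 2Cov(ΔTC,ΔHDL) - (2/5)Cov(ΔTC,ΔTG) + (2/5)Cov(ΔHDL,ΔTG), and the plan reports no covariances. The confidence interval and individual values are lost with it.

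**3. Precision of a directly reported LDL change.** Half-width of the 95% CI = t × SD/√n. The SD of change is assumed to be 15 to 35 mg/dL. The n values are 30 (maximum enrolment) and 22 (10% of 220 invited).
- n = 30: 2.045 × 15/√30 = 5.6; with SD 35, 13.1.
- n = 22: 2.080 × 15/√22 = 6.7; with SD 35, 15.5.

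**4. Effect of treatment after results.** If k people start medication and LDL falls by f in each, the mean shifts by k × f/n. For k = 1 to 3 and f = 30 to 50 (assumptions):
- n = 30: 1 × 30/30 = 1.0 to 3 × 50/30 = 5.0.
- n = 22: 1 × 30/22 = 1.4 to 3 × 50/22 = 6.8.

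This is why LDL should be read beside medication changes.

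**5. Checklist timing.** Put session 1 at week 0. Session k falls at week k - 1 if strictly weekly, or at (k - 1) × 26/15 if 16 sessions fill 26 weeks. Session 15 is then at week 14 or week 24.3.
- The baseline survey precedes the diet.
- First on-diet checklist window: opens at 14 - 1 = week 13 at the earliest.
- One-month free-text item: opens at (98 - 30)/7 = week 9.7 at the earliest.
- Overlap of either window with the first 2, 4, 6 or 8 weeks: 0 days.
- Narrative 5.1 phases the diet in one meal per week. Taking 3 weeks for that (assumption) plus a couple of weeks, symptoms would end near week 5. Stretching the early period to 8 weeks after that start gives 3 + 8 = week 11. The checklist still misses it; the free-text item touches only the last 11 - 9.7 = 1.3 weeks.

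**6. Could the early weeks still be surveyed?** The SAP is dated 20 April 2021, and the data range in IRB application 13.15 ends in December 2021. If 12-month follow-up ends within that range (inference; no start date is given), session 1 was no later than 31 December 2020, which is 110 days or 15.7 weeks before the SAP date. Sessions 2, 4 and 6 (weeks 1, 3 and 5 if weekly; 1.7, 5.2 and 8.7 if spread) would have passed.

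**The case against.** A reader might infer that an LDL rise would go unseen. The documents do not support that. Narrative 6.0 monitors lipids at all three time points and sends results to participants and their primary care providers. The Abstract and narrative 5.5 speak of lipids in general, and the SAP summarises every continuous outcome, so an LDL summary is permitted. Aim 2, if followed, yields the mean approximately. All of this stands. What remains is that no outcome passage commits to LDL, and its spread cannot be rebuilt from the lipids that are named.

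A reader might also infer that early side effects will not be recorded, or will certainly be undercounted. That goes too far as well. The study team agrees to report all adverse events, complaints and problems (IRB application 9.10). Participants can speak with study staff and physicians (narrative 5.1). The surveys are to include self-reported side effects (IRB application 13.10; narrative 5.5). A SAP item asks, with no recall limit, what about health worsened on the food plan. Interviews treat side effects as a barrier, with up to 30 interviewees in IRB application 6.42 but 14 in narrative 5.5. Reasons for withdrawal are documented (IRB application 9.7). These channels are spontaneous, retrospective, or not visible in wording and recall period, so the supportable statement is that early symptoms may be undercounted.

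It is also fair that the primary outcomes are feasibility and acceptability, that early tolerability rates are not a stated aim, and that the lipid values above show what is possible rather than how large it is. Extra early questionnaires could burden a study that measures retention by survey completion. These points keep the priority down and shape the fix.

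**Conclusion.** Both parts hold, within limits. The lipid outcome as defined does not name a lipid risk that the protocol itself states. The ratio and triglycerides can improve while LDL changes by +1.5 or +18 mg/dL (hypothetical values, assumed LDL formula). Reporting all three Aim 2 lipids on the same participants would restore the approximate mean but not the SD, confidence interval or individual values. The readable symptom checklist has no overlap with the first 8 weeks from session 1, whether sessions are strictly weekly or spread over 6 months. Part of this rests on what can be read: a separate side-effect item may exist whose wording is not visible.

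The gap is in reporting. Clinical monitoring of lipids is not affected, and nothing already planned becomes invalid. Priority: low to moderate.

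**What to change.** **(a) LDL.** Reconcile Aim 2 and the Secondary Measures definition with the general lipid wording in the Abstract and in Laboratory metrics, and name LDL. Report its change at 6 and 12 months as mean, SD, 95% CI and individual values, beside the medication changes already surveyed at both times. This needs no new data: the panels are drawn and the medication items are in the SAP survey. Intervals will be wide, as shown above.

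**(b) Symptoms.** Do not present the 6- and 12-month checklist results as early tolerability. Tabulate recorded withdrawal reasons and reported adverse events, and state that early side-effect rates are not estimated. This also needs no new data.

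**(c) Only if early sessions are still ahead.** Give the existing checklist at a few early sessions that participants already attend, for example 2, 4 and 6. Keep it separate from the 6- and 12-month surveys that define retention. Report the number with each symptom over the number responding, with an exact 95% CI and the number enrolled. The cost is an amendment and some participant burden. Precision would be modest: 9/30 gives 14.7% to 49.4%, 7/22 gives 13.9% to 54.9%, and zero events give an upper limit of 11.6% (n = 30) or 15.4% (n = 22). On the calendar inference above, this option has probably lapsed.

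**(d) Consistency.** IRB application 8.2 excludes people with LDL above 190; the narrative criteria in 5.1 and 5.4 do not list this. The passages must be reconciled, and until then any count above that value is descriptive only.

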Change in body weight: Body weight will be measured and recorded at each attended session. We will calculate average body weight change and percent body weight loss at the end of the program's core phase (6 months) and maintenance phase (12 months). Among session non-attendees, we will attempt to schedule 6- and 12-month weigh-ins at participants' convenience within 2 weeks of the final core and maintenance sessions. All weights will be obtained using the same calibrated scale.

Change in HbA1c: We will calculate change in HbA1c from baseline to 6 and 12 months

Change in lipids: We will calculate change in triglycerides and total cholesterol/HDL ratio from baseline to 6 months and 12 months.

Change in survey measures: We will calculate change in self-reported survey measures from baseline to 6 months and 12 months.

Fidelity: We will measure intervention fidelity (i.e., extent to which components of an intervention are delivered as intended) using quantitative measures adapted from the literature²⁶ as well as qualitative interview feedback from participants and dietitians.

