your			Score:	files/attac
physical			Sum	hments/p
health?			responses	dfs/PROM
In	Q4		to 3, 6, 7,	ISGlobalH
general,			8.	ealthScale
how			Fatigue	V1.0-
would			on	1.1.pdf
you rate			average,	
your			pain on	
mental			average,	
health,			extent to	
including			carry out	
your			physical	
mood and			activities,	
your			how	
ability to			would	
think?			you rat	

In general, how would you rate your satisfaction with your social activities and relationships?

Q5

your physical health.

Global Mental Health score:
SUM: 2, 4, 5, 10
How often bothered by

In general, please rate how well you carry out your usual social activities and roles. (This includes activities at home, at work and in your community, and responsibilities as a parent, child, spouse, employee, friend, etc.)

Q6

emotional problems, rate your mental health, rate your satisfaction, quality of life.

To what extent are you able to carry out your everyday physical activities such as walking, climbing stairs, carrying groceries, or moving a chair? Q7

5- Completely
4- Mostly
3- Moderately
2- A little
1- Not at all

In the past 7 days:

How often have you been bothered by emotional problems such as feeling anxious, depressed, or irritable? Q8

5- Never
4- Rarely
3- Sometimes
2- Often
1- Always

How would you rate your fatigue on average? Q9

5- None
4- Mild
3- Moderate
2- Severe
1- Very severe

How would you rate your pain on average?	Q10	Answer choices 0 through 10 with anchors on 0, 10: 0- No pain 1 2 3 4 5 6 7 8 9 10- Worst pain imaginable
--	-----	--

Program Evaluation

How would you rate your overall satisfaction with the program?	Q1	Answer choices 1-7 with anchors on 1,7: 1- Not at all satisfied 2 3 4 5 6 7- Very satisfied	NA	NA
If a friend were in need of similar	Q2	1- No, definitely not 2- No, not		

What's the most meaningful thing you've learned or gotten out of this program?

Q3

Participants may enter free text of whatever they choose.

How helpful have the classes been?

Q4

Answer choices 1-7 with anchors on 1,7:
1- don't include them, they were not helpful
2
3
4
5
6
7- you must include them, they were very helpful

Do you have any suggestions about how we can improve the classes? Which were your favorite or least favorite topics?

Q5

Participants may enter free text of whatever they choose.

How helpful were the handouts? How much would you recommend that we include them in the next study?

Q6

Answer choices 1-7 with anchors 1,7:
1- don't include them, they were not helpful
2
3
4

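### The PROMIS Global Health scoring key uses item numbers that do not match the SAP's own Q1-Q10 numbering or the item names beside them

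*SAP*

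**What the plan says.** The block headed Global Health PROMIS Questionnaire in the SAP's survey scoring table numbers ten items. Q2 is quality of life, Q3 physical health, Q4 mental health, Q5 satisfaction with social activities and relationships, and Q6 social activities and roles. The next three are:

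- "To what extent are you able to carry out your everyday physical activities such as walking, climbing stairs, carrying groceries, or moving a chair? Q7"
- "How often have you been bothered by emotional problems such as feeling anxious, depressed, or irritable? Q8"
- "How would you rate your fatigue on average? Q9"

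The last item, Q10, is "How would you rate your pain on average". It has its own response scale: "Answer choices 0 through 10 with anchors on 0, 10: 0- No pain". Every other item used here is answered 1-5, with 5 the best state.

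The scoring key in the same block does three things:

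- It recodes an item it calls Q7 and describes as average pain, mapping 0 to 5, 1-3 to 4, 4-6 to 3, 7-9 to 2 and 10 to 1.
- It forms Global Physical Health by summing 3, 6, 7 and 8, and names fatigue, pain, physical activities and physical health.
- It forms the mental score as "Global Mental Health score: SUM: 2, 4, 5, 10 How often bothered by" "emotional problems, rate your mental health, rate your satisfaction, quality of life".

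Protocol section 5.5 lists the survey measures among the secondary measures: "We will calculate change in self-reported survey measures from baseline to 6 months and 12 months". The SAP's quantitative analysis applies paired t-tests to all continuous outcomes.

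**The concern.** The numbers and the names in the key select different items, and nothing in either document says that the key uses another item order. An analyst has some reason to trust the numbers: in the Treatment Self-Regulation Questionnaire block of the same table, the key's numbers do refer to the survey's own Q1-Q15.

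This key is the only scoring instruction the documents give for the two scores. If it is coded by number, the physical score takes social roles and emotional problems in place of fatigue and pain, and the mental score takes pain in place of emotional problems. If the recode is also applied by number, it falls on a 1-5 function item and pain enters the mental score unrecoded. Reported changes at 6 and 12 months would then describe something other than physical and mental health.

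**Working it through.** **Step 1. Map the key's names to the survey's numbers.** All inputs come from the PROMIS block of the SAP table.

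| Key entry | Numbers in key | Names in key, as survey numbers | In key only | In names only |
|---|---|---|---|---|
| Recode (pain) | Q7 | Q10 | 7 | 10 |
| Physical sum | 3, 6, 7, 8 | 3, 7, 9, 10 | 6, 8 | 9, 10 |
| Mental sum | 2, 4, 5, 10 | 2, 4, 5, 8 | 10 | 8 |

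Five of the eight summed numbers (3 and 7; 2, 4 and 5) agree with the names. The wrong entries are 6 and 8 in the physical sum, 10 in the mental sum, and Q7 in the recode.

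**Step 2. Write out three readings.** Let r() be the recode map.

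- By name: physical = Q3 + Q7 + Q9 + r(Q10); mental = Q2 + Q4 + Q5 + Q8.
- Mixed (pain recoded by name, sums by number): physical = Q3 + Q6 + Q7 + Q8; mental = Q2 + Q4 + Q5 + r(Q10).
- Strictly by number: physical = Q3 + Q6 + r(Q7) + Q8; mental = Q2 + Q4 + Q5 + Q10, with Q10 left on 0-10.

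**Step 3. Score ranges**, with Q2-Q9 in 1-5 and Q10 in 0-10. On answers 1, 2, 3, 4, 5 the recode returns 4, 4, 4, 3, 3, so r(Q7) lies between 3 and 4.

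- By name: 4 × 1 = 4 to 4 × 5 = 20 for both scores.
- Mixed: 4 to 20 for both scores.
- Strictly by number: physical from 1 + 1 + 3 + 1 = 6 to 5 + 5 + 4 + 5 = 19; mental from 3 + 0 = 3 to 15 + 10 = 25.

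**Step 4. Effect of moving one item, the others held fixed.** The sums are additive, so these changes do not depend on the other answers.

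| Change | By name | Mixed | Strictly by number |
|---|---|---|---|
| Fatigue improves, 2 to 4 | physical +2 | none | none |
| Emotional problems improve, 2 to 4 | mental +2 | physical +2 | physical +2 |
| Pain falls, 6 to 2 | physical +1 (r: 3 to 4) | mental +1 | mental -4 |
| Physical function improves, 2 to 5 | physical +3 | physical +3 | physical -1 (r: 4 to 3) |

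**Step 5. Extremes under the strict reading.** For best possible health (Q2-Q9 = 5, pain = 0), mental = 15 + 0 = 15. For worst possible health (Q2-Q9 = 1, pain = 10), mental = 3 + 10 = 13. By name the same two states score 20 and 4. The strict mental score therefore separates the best and worst states by 2 points instead of 16.

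**The case against.** The strongest reply is that the answer already stands beside the error. The names give a complete and unambiguous key, so an analyst working from them scores correctly. This is right, and it limits the consequence: a wrong score arises only if the numbers are followed.

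Second, the strict reading is the least plausible one. It requires ignoring the word pain in the recode instruction and applying a 0-10 map to an item answered 1-5. This also stands. The sign reversals and the 6-19 and 3-25 ranges belong to that reading alone. The mixed reading is milder: pain keeps its direction but lands in the wrong score, emotional problems and social roles count as physical health, and fatigue is lost. It is also harder to detect, because both scores stay within 4-20.

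Third, the numbers would fit the names under another item order (6 = physical activities, 7 = pain, 8 = fatigue, 10 = emotional problems). The key may therefore be consistent within a different numbering of the instrument. That would explain the slip, but the SAP neither reproduces nor refers to such an order.

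Finally, the reach is small: this is one of several survey measures in a single-arm pilot of up to 30 people, and stored raw items allow rescoring.

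A layout fault from PDF extraction does not explain the mismatch. Q7, Q8 and Q9 sit with their full item text, the 0-10 scale sits with Q10, and the key itself attaches pain to Q7.

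**Conclusion.** The concern holds and is minor. The key contradicts the survey's numbering in the recode line and in three of its eight summed items. Scored by number, two of four physical items and one of four mental items are wrong, and fatigue is dropped altogether. The damage runs from undetectable misallocation within 4-20 (mixed reading) to reversed changes in pain and function (strict reading). None of it occurs if the analyst works from the names.

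The conclusion assumes that the names express the intended scoring, which the 0-10 recode map supports because it fits only Q10. Feasibility, acceptability, weight, A1c and lipids are not affected.

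**What to change.** Before scoring, rewrite the key in the survey's own numbering, using the names the SAP already gives:

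- Recode Q10 (pain).
- Global Physical Health = Q3 + Q7 + Q9 + recoded Q10.
- Global Mental Health = Q2 + Q4 + Q5 + Q8.

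If the sponsor prefers to keep the present numbers, the SAP must state the item order they refer to and how it maps to Q1-Q10. If scores have already been computed, confirm which reading the code used and rescore from the raw items where needed. The cost is a few lines of SAP text and scoring code, with no change to data collection.
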